15.5 APPENDIX 5: CURIE & SIOPEN SCORING METHODS FOR NEUROBLASTOMA

Figures 2A & 2B:

[figure not shown]

Figure 2A; The Curie method. This method divides the skeleton into nine segments to view osteomedullary involvement and adds a tenth sector that counts any soft tissue involvement to the score. The extension score for this method is graded as: 0. no sites per segment; 1. one site per segment; 2. more than one site per segment; and 3. diffuse involvement (>50% of the segment). The intensity score is graded as: 0. for no uptake; 1. for doubtful uptake; 2. for definite uptake less than liver; and 3. for intense uptake greater than that of liver. Thus, the maximum score for either extension or intensity would be 30. The Curie score has been shown to have a good inter-observer concordance of 92 and 95% in two independent studies. It has been validated in France and is now widely used in North America for the New Approaches to Neuroblastoma Therapy consortium and the Children's Oncology Group (COG).

Figure 2B: The SIOPEN method: the skeletal distribution of *m*IBG is recorded in 12 anatomical body segments as follows: skull, thoracic cage, proximal right upper limb, distal right upper limb, proximal left upper limb, distal left upper limb, spine, pelvis, proximal right lower limb, distal right lower limb, proximal left lower limb and distal left lower limb. The extent and pattern of skeletal *m*IBG involvement is scored using a 0–6 scale to discriminate between focal discrete lesions and patterns of more diffuse infiltration. Each segment is scored as 0. no involvement; 1. one discrete lesion; 2. two discrete lesions; 3. three discrete lesions; 4. > 3 discrete foci or a single diffuse lesion involving < 50% of a bone; 5. diffuse involvement of > 50 to 95% of an entire bone; 6, diffuse involvement of the entire bone, with a maximum score of 72. The SIOPEN score is the current method being used in Europe for a prospective phase 3 neuroblastoma trial.

CANCER RESEARCH UK Statistical Analysis Plan

A Cancer Research UK Phase I/II study to compare $[^{124}\text{I}]m\text{IBG}$ PET/CT to $[^{123}\text{I}]m\text{IBG}$ imaging in patients with metastatic neuroblastoma.

Sponsor protocol number: CRUKD/12/002

EudraCT number: 2012-002029-31

Chief Investigator:

[name]
Nuclear Medicine and PET
Department
Royal Marsden Hospital

[REDACTED]
[REDACTED]
[REDACTED] [REDACTED]
[REDACTED]

Sponsor:

Cancer Research UK
Centre for Drug Development

[REDACTED]
[REDACTED]

1.1 Protocol Synopsis and Background

Full Title: A Cancer Research UK Phase I/II study to compare [¹²⁴I]meta-Iodobenzylguanidine (mIBG) positron emission tomography/computerised tomography (PET/CT) to [¹²³I]mIBG imaging in patients with metastatic neuroblastoma.

Short Title: A Phase I/II study of [¹²⁴I]mIBG PET/CT in neuroblastoma.

This is a multi-centre, non-therapeutic Phase I/II study directly comparing [¹²⁴I]mIBG positron emission tomography/computerised tomography (PET/CT) and conventional [¹²³I]mIBG imaging in patients with newly diagnosed, relapsed or refractory metastatic neuroblastoma. A minimum of nine evaluable patients will be scanned at two centres in the UK.

1.2 Clinical Study Objectives and Endpoints

Primary objective	Endpoint
1. To show that [¹²⁴ I]mIBG PET/CT can detect an equal or greater number of neuroblastoma lesions compared to conventional [¹²³ I]mIBG planar scintigraphy.	1. Comparison of the percentage of lesions detected as positive by [¹²³ I]mIBG planar scintigraphy which are also considered positive with [¹²⁴ I]mIBG PET/CT.

Secondary objectives	Endpoints
1. To show that [¹²⁴ I]mIBG PET/CT can detect an equal or greater number of neuroblastoma lesions compared to conventional [¹²³ I]mIBG scintigraphy with 3D imaging by SPECT (single photon emission computerised tomography).	1. Comparison of the percentage of lesions detected as positive by [¹²³ I]mIBG SPECT which are also considered positive with [¹²⁴ I]mIBG PET/CT.
2. Assessing the safety and toxicity profile of a single intravenous administration of [¹²⁴ I]mIBG.	2. Determining the causality of each adverse event to [¹²⁴ I]mIBG and grading

Secondary objectives	Endpoints
	severity according to National Cancer Institute Common Toxicity Criteria for Adverse Events (NCI CTCAE) version 4.02.

Tertiary objectives	Endpoints

[REDACTED]
 
[REDACTED]
 
[REDACTED]
 
[REDACTED]
 
[REDACTED]
 
[REDACTED]
	
[REDACTED]
 
[REDACTED]
 
[REDACTED]
 
[REDACTED]
 
[REDACTED]
 
[REDACTED]

[REDACTED]
 
[REDACTED]
 
[REDACTED]
	
[REDACTED]
 
[REDACTED]
 
[REDACTED]
 
[REDACTED]

[REDACTED]
 
[REDACTED]
 
[REDACTED]
 
[REDACTED]
	
[REDACTED]
 
[REDACTED]
 
[REDACTED]
 
[REDACTED]
 
[REDACTED]

[REDACTED]
 
[REDACTED]
 
[REDACTED]
 
[REDACTED]
 
[REDACTED]
	
[REDACTED]
 
[REDACTED]
 
[REDACTED]
 
[REDACTED]
 
[REDACTED]
 
[REDACTED]

Tertiary objectives	Endpoints

[REDACTED]
 
[REDACTED]
 
[REDACTED]
 
[REDACTED]
 
[REDACTED]
 
[REDACTED]
 
[REDACTED]
 
[REDACTED]
	
[REDACTED]
 
[REDACTED]
 
[REDACTED]
 
[REDACTED]
 
[REDACTED]
 
[REDACTED]

[REDACTED]
 
[REDACTED]
 
[REDACTED]
	
[REDACTED]
 
[REDACTED]
 
[REDACTED]
 
[REDACTED]

1.3 Study Design

This is a multi-centre, non-therapeutic Phase I/II study directly comparing [¹²⁴I]mIBG PET/CT and conventional [¹²³I]mIBG imaging in patients with newly diagnosed, relapsed or refractory metastatic neuroblastoma. The study uses a modified Simon two-stage phase II design.

Patients who require routine conventional [¹²³I]mIBG planar scintigraphy as a means of assessing response to their ongoing treatment or for staging of their disease will be recruited. The majority of patients will also be planned to undergo 3D imaging by single-photon emission computed tomography (SPECT) as part of routine care where this is available. Additional [¹²⁴I]mIBG PET/CT imaging will take place approximately 3 to 21 days after routine [¹²³I]mIBG imaging and before the commencement of any new anti-cancer therapy.

There is one planned interim analysis which will be performed after a minimum of 50 lesions have been identified by [¹²³I]mIBG planar scintigraphy from a minimum of 9 evaluable patients

1.4 Number of Subjects

The primary endpoint of the study is the percentage of lesions identified as positive using [¹²³I]mIBG planar scintigraphy which are also identified as positive on [¹²⁴I]mIBG PET/CT. The definition of a positive lesion is described in Section 9.1 of the clinical study protocol. The aim is to prove that there is more than 90 % agreement between the methods, with an expected level of agreement of 97 %. Patients are anticipated to have a median of 3 lesions. Lesions are assumed to be independent within patients for the primary analysis. The following two stage design will be used, where the true proportion of agreement is denoted by p .

In the first stage, a total of at least 9 evaluable patients will be recruited, with a combined total of at least 50 lesions positive on [¹²³I]mIBG PET/CT. Initially an exact one-sided binomial test of the null hypothesis: $p \geq 97\%$ will be done using $\alpha = 0.05$. If this is rejected in favour of the alternative hypothesis $p < 97\%$, the study will be stopped early for futility. With a total of exactly 50 lesions this will occur if 45 or fewer lesions are also positive on [¹²⁴I]mIBG PET/CT.

If the null hypothesis is accepted, a further one-sided binomial test of the null hypothesis, $p \leq 90\%$ will be done using $\alpha = 0.025$. If this is rejected in favour of the alternative hypothesis $p > 90\%$ then the study may be stopped early for efficacy. With a total of 50 lesions this will occur only if all 50 lesions are also positive on [¹²⁴I]mIBG PET/CT. If this null hypothesis is not rejected, the study will continue to the second and final stage.

Only if following the interim analysis recruitment is to continue, a second stage will be required and will end when an overall total of at least 33 evaluable patients with at least 100 lesions have been recruited. An exact one-sided binomial test of the null hypothesis, $p \leq 90\%$, will be done using $\alpha = 0.025$. If this is rejected in favour of the alternative hypothesis $p > 90\%$ then the study will be declared a success. With a total of 100 lesions this will occur if at least 96 lesions are also positive on [¹²⁴I]mIBG PET/CT.

The overall study design including the second stage has 82 % power and an α of 0.03. If the true percentage of agreement is 97 % then there is a 22 % chance of stopping early for efficacy; if the true percentage of agreement of 90% then there is a 57 % chance of stopping early for futility. The total sample size of 100 lesions was calculated based on a single stage A'hern design with $p_0 = 0.90$ and $p_1 = 0.97$, and the overall power and α has been calculated based on exact binomial probabilities.

2 Analysis Sets

2.1 Definition of Analysis Sets

The following trial populations have been defined for reporting purposes:

- Full Analysis Population: All patients enrolled to the study.
- Safety [^{123}I]mIBG Population: All patients who receive [^{123}I]mIBG (these patients may or may not have received [^{124}I]mIBG).
- Safety [^{123}I]mIBG and [^{124}I]mIBG Population: All patients who receive both [^{123}I]mIBG and [^{124}I]mIBG.
- Evaluable Population: Patients who received both [^{123}I]mIBG and [^{124}I]mIBG and underwent trial scanning with both agents. All lesions from these patients are considered independent of one another.
- [REDACTED]
- A sensitivity analysis will be informed in those in the evaluable population and have less than 10 lesions.

The primary analysis set will consist of all patients consented to the study, with at least one positive lesion recorded on routine [^{123}I]mIBG planar scintigraphy, who have also completed [^{124}I]mIBG PET/CT within 3 to 21 days as planned i.e. the Evaluable Population. Patients who did not undergo both [^{123}I]mIBG planar scintigraphy and [^{124}I]mIBG PET/CT will be excluded from this set, as will any patient where zero positive lesions were found on [^{123}I]mIBG planar scintigraphy, and patients with more than 21 days between [^{123}I]mIBG and [^{124}I]mIBG scans.

The safety analysis set for the secondary objective will consist of all patients consented to the study who received any dose of [^{124}I]mIBG at any time whether or not they subsequently completed any of the planned imaging procedures i.e. the Safety [^{123}I]mIBG and [^{124}I]mIBG Population. Additionally, all AEs occurring post consent and prior to [^{124}I]mIBG will be summarised (including those occurring post [^{123}I]mIBG administration).

2.2 Violations and deviations

Taking the date of [^{123}I]mIBG scan as Day 0, patients whose [^{124}I]mIBG scans takes place on Day 22 or more will be excluded from the primary analysis set, but included in the safety set.

Patients who do not receive the planned injection of [^{124}I]mIBG will not be included in any statistical analysis, however their safety data will be summarised as described in Sections 2.1 and

3 3.1.5. Primary and Secondary endpoints

Each evaluable study patient will be assessed for disease using up to five different modalities:

[^{124}I]mIBG PET/CT (the experimental modality)

[^{123}I]mIBG planar scintigraphy (the primary comparator)

[^{123}I]mIBG planar scintigraphy + SPECT (a secondary comparator)

On each modality (unless otherwise stated), each of the following endpoints is recorded. [^{124}I]mIBG PET/CT and [^{123}I]mIBG planar scintigraphy results will be assessed by an agreed number of observers independently who will record all relevant endpoints as listed below. Prior to the interim analysis, the observers will meet to establish a consensus opinion and record their agreed consensus endpoints for each patient. The same procedure will take place prior to the final analysis, for all scans which had not previously been included in the interim analysis.

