3.2 PATIENT EVALUABILITY

To be evaluable for the primary imaging analysis a patient must be eligible for the study, receive [¹²³I]mIBG and undergo planar scintigraphy, fulfil the clinical criteria for [¹²⁴I]mIBG imaging, receive [¹²⁴I]mIBG and complete the required PET/CT scanning schedule in accordance with the Study Imaging Manual. Any patient who is not evaluable for the primary imaging analysis will be replaced.

To be evaluable for the assessment of toxicity a patient must have received [¹²⁴I]mIBG.

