5.3 DOSE SCHEDULE

Patients will receive one intravenous injection of [¹²⁴I]mIBG Solution for Injection on Day 1.

All patients will receive a minimum injected dose of 10 MBq and a maximum injected dose of 50 MBq [¹²⁴I]mIBG equating to a maximum chemical dose of 10 µg of stable mIBG. The maximum activity administered to adult patients will be 50 MBq. This maximum activity, 50 MBq, will be requested for each adult patient as the specified target dose. On occasions that the maximum activity, 50 MBq, is not met, but is still within the required range of 10 to 50 MBq, patient administration will proceed and the scanning time adjusted accordingly. The maximum activity to paediatric patients will be scaled by weight based upon the EANM paediatric dose card (Lassmann, Biassoni et al. 2007). This maximum activity will be requested for each paediatric patient as the specified target dose. With reference to the EANM scheme, a baseline activity of 3.5 MBq, a minimum activity of 10 MBq and class B scaling factors are deemed appropriate. This will result in an administered activity between 10 MBq and 50 MBq depending on the patient's weight.

Administration of [¹²⁴I]mIBG Solution for Injection on Day 1 will be approximately 3-21 days after the routine [¹²³I]mIBG scan. A minimum interval of 72 hours is required between injection of [¹²³I]mIBG tracer and the [¹²⁴I]mIBG PET/CT scan. There is no minimum interval between patients.

The scanning schedule will take between approximately 30 and 75 minutes depending on whether the scanning time is to be adjusted to account for administration of lower activity than specified target dose. If the scan schedule is likely to exceed 75 minutes then this should be discussed with the patient prior to the injection of [¹²⁴I]mIBG to seek verbal consent. Any discussions should be documented in the patients' medical notes.

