7.3 EVALUATIONS DURING THE STUDY (DAY -21 TO -3)

- Administration of thyroid blockade given in accordance with local standard operating procedure for diagnostic use of [¹²³I]mIBG
- Administration of [¹²³I]mIBG
- [¹²³I]mIBG planar scintigraphy with 3D SPECT as available, performed for the routine assessment of neuroblastoma. N.B. This should be performed following an interval of at least 7 days from previous anti-cancer therapy between Day -21 to Day -3.

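### Protocol and SAP disagree on where the 3-21 day interval ends, so the SAP's hard scan-to-scan cut-off could exclude a patient imaged on the earliest permitted planar day

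*Combined protocol and SAP*

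**What the plan says.** **Schedule.** Protocol 7.3 places the planar scan "between Day -21 to Day -3". Protocol 1.3 gives the same window for the scan, with the [123I]mIBG injection one day earlier. Protocol 5.3 says that the [124I]mIBG injection on Day 1 "will be approximately 3-21 days after the routine" [123I]mIBG scan. Protocol 7.6.1 and footnote j of 7.9 put PET/CT on Day 2, at 24 h ± 3 h after the injection.

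**Other wording of the interval.** Protocol 1.2, 2.6 and 3.3, and SAP 1.3, apply approximately 3-21 days to the interval from routine imaging to the PET/CT imaging, not to the injection.

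**Analysis set.** SAP 2.1 removes from the primary set "patients with more than 21 days between" the two scans. SAP 2.2 sets the origin, "Taking the date of [^{123}I]mIBG scan as Day 0", and says that patients whose [124I]mIBG "scans takes place on Day 22 or more will be excluded from the primary analysis set".

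**Evaluability.** Protocol 3.2 requires, among other things, that the patient "complete the required PET/CT scanning schedule in accordance with the Study Imaging Manual". Its text gives no maximum interval between the scans. Protocol 5.5 on replacement does not mention the interval.

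**The concern.** The same figure of 21 days is used for two intervals that differ by one day: planar scan to injection, and planar scan to PET/CT. A site following 5.3 and 7.3 can image a patient on Day -21, inject on Day 1, scan on Day 2 and be within the schedule. The SAP would then drop that patient and all of that patient's lesions from the primary analysis.

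The counts could also diverge. Both the interim and the end of stage 2 depend on a number of evaluable patients (9 and 33). On the text of protocol 3.2 this patient is evaluable and need not be replaced; under the SAP's primary set the patient is not there. The interim could be triggered on 9 patients and run on 8.

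**Working it through.** **1. Day numbering.** Protocol 7.6.1 heads the first thyroid blockade dose Day -1 and describes it as the day before the Day 1 injection. There is therefore no Day 0, and the interval from Day -a to Day b is a + b - 1 days.

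**2. Reproduce the protocol's figure.** Planar scan to injection (b = 1) is a + 1 - 1 = a days. For Day -3 to Day -21 this gives 3 to 21 days, exactly the interval in protocol 5.3.

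**3. Planar scan to PET/CT.** With b = 2 the interval is a + 2 - 1 = a + 1 days, so the range is 4 to 22 days.

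**4. Apply the SAP rule.** Exclusion at 22 days or more means a + 1 ≥ 22, so a ≥ 21.

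| Planar scan | To injection (Day 1) | To PET/CT (Day 2) | SAP 2.1/2.2 |
|---|---|---|---|
| Day -21 | 21 days | 22 days | excluded |
| Day -20 | 20 days | 21 days | kept |
| Day -3 | 3 days | 4 days | kept |

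Day -21 to Day -3 contains 19 days, and one of them is affected.

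**5. Two variants.**
- If a Day 0 is counted, planar scan to PET/CT is 5 to 23 days. Day -21 (23 days) and Day -20 (22 days) are both excluded. However, planar scan to injection becomes 4 to 22 days, which no longer matches 5.3, so numbering without a Day 0 fits the protocol better.
- If the [123I]mIBG injection must itself fall within Day -21 to -3, the earliest scan is Day -20. With no Day 0, PET/CT is then 21 days later and nobody is lost.

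**6. Weight of one patient.** At the interim, one patient is 1/9 = 11% of patients and, if 50 lesions come from 9 patients, on average 50/9 = 5.6 lesions. At the end, one patient is 1/33 = 3% of patients, and the expected median is 3 lesions per patient.

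**7. Design figures.** The check uses exact binomial probabilities with 50 lesions at stage 1, futility at 45 or fewer, efficacy at 50 of 50, and success at 96 or more of 100. This gives power 0.8215 at 97% agreement (stated 82%), alpha 0.0266 at 90% (stated 0.03), early efficacy 0.218 (stated 22%) and early futility 0.569 (stated 57%). The stated figures reproduce. With other final lesion totals, keeping alpha at 0.025 for the final test:

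| Final lesions | Power at 97% |
|---|---|
| 103 | 0.807 |
| 100 (96 needed) | 0.822 |
| 99 (96 needed) | 0.667 |
| 97 (94 needed) | 0.679 |

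**The case against.** The strongest reply is that the SAP follows the protocol. Sections 1.2, 2.6 and 3.3 all measure to the PET/CT imaging, and SAP 2.1 describes its window as the planned one. Only 5.3 ties the 21 days to the injection. A strict limit on the time between two scans that are being compared is also a defensible analysis choice. This stands to the extent that the fault is an inconsistency within the protocol, not a plain departure by the SAP. It does not remove the conflict: those sections say approximately, the SAP has a hard limit, and section 3.3 itself sends the reader to 7.9 for the detailed timing.

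Second, 7.3 and the table in 7.9 put the [123I]mIBG injection in the same Day -21 to -3 window as the scan. Read strictly, with the injection one day before the scan, that rules out a Day -21 scan. This also stands as a possible reading, but 1.3 and the note in 7.3 apply the window to the scan itself, so a Day -21 scan is permitted there.

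Third, protocol 3.2 refers to a Study Imaging Manual that is not among the documents and might set an interval. One can say only that the patient meets the text of 3.2 as written.

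Fourth, SAP 1.4 ends stage 2 on evaluable patients, and SAP 2.1 equates the primary set with the Evaluable Population, so under the SAP's own count an excluded patient would not have been counted. That is fair, but the bullet in SAP 2.1 that defines the Evaluable Population carries no interval limit, and protocol 12.2 has the study manager declare when the interim conditions are met. Which definition governs the trigger is not stated.

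**Conclusion.** The inconsistency is real and small. Where the planar scan is on Day -21, as protocol 1.3 and 7.3 allow, PET/CT on Day 2 falls 22 days later. SAP 2.1 and 2.2 would then exclude a patient who meets the protocol schedule and the stated text of 3.2, and who may still count towards 9 or 33. This rests on there being no Day 0 and on the Day -21 to -3 window applying to the scan.

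A reader might infer that compliant patients are in fact being lost. The documents do not show this: they give no distribution of intervals, 1 day in 19 is not a probability, and the number affected may be zero.

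A reader might also take the fall from 82% power at 100 lesions to 68% at 97 as the price of losing one median patient. It is not. Dropping a single lesion, to 99, gives 67%, and 103 lesions give 81%, so the fall is mainly the discreteness of the exact test when the total is exactly 100. The plan requires at least 100 lesions, so that total need not occur. No loss of power should be claimed.

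**What to change.** State once whether the interval runs to the injection or to the PET/CT, and use the same end point in protocol 1.2, 1.3, 2.6, 3.3, 5.3, 7.3 and 7.9. At the same time, say whether the Day -21 to -3 window applies to the planar scan or also to the [123I]mIBG injection. Which interval is appropriate is for the trial team to decide; the analysis rule should follow that decision.

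Then word the exclusion in SAP 2.1 and 2.2 so that no patient who keeps to the schedule is dropped. If the current schedule stands, this means excluding only PET/CT on Day 23 or later with the planar scan as Day 0. Because PET/CT is one day after injection, that is the same as more than 21 days from planar scan to injection.

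Put the same evaluability rule in protocol 3.2, and use it for the interim and final counts, so that the trigger and the analysis set agree.

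The cost is SAP wording plus a minor protocol amendment, because a change to 3.2 cannot be made in the SAP alone. No visit or scan needs to change if the current schedule is kept. The SAP addendum refers to a statistical report reviewed in November 2020. If the primary analysis has already been run, report how many patients had a 22-day interval and, if there were any, give the result with and without them.

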3.1.1 Total number of positive lesions recorded

The total number of lesions will be provided to the Statistician via validated listings from the Sponsor. Data will be recorded in the eCRF by the Trial Manager at the Central Imaging Unit and Source Data Verified (SDV'd) by a Sponsor Clinical Research Associate. The Sponsor Clinical Study Manager will perform a data review before the eCRF is locked and listings are provided to the Statistician.

In summary, the following data will be provided to the Statistician for each evaluable patient for each imaging modality as calculated by each individual Reviewer and as a consensus:

- Number of lesions in each skeletal segment and total number of lesions using the CURIE method (i.e. all lesions with a score of 4 or 5) and also:
 - Total number of lesions with a confidence score of 1
 - Total number of lesions with a confidence score of 2
 - Total number of lesions with a confidence score of 3
 - Total number of lesions with a confidence score of 4
 - Total number of lesions with a confidence score of 5
- Number of lesions in each skeletal segment and total number of lesions using the SIOPEN method (i.e. all lesions with a score of 4 or 5) and also:
 - Total number of lesions with a confidence score of 1
 - Total number of lesions with a confidence score of 2
 - Total number of lesions with a confidence score of 3
 - Total number of lesions with a confidence score of 4
 - Total number of lesions with a confidence score of 5

For example, one Patient's PET/CT scan will have the data above provided but as three or more sets (for detail of the number of reviewers, see the Imaging Review Manual):

- Reviewer 1's data set
- Reviewer 2's data set
- Consensus data set

